- Additional arguments amongst those stated before, like alternative explanation (e.g. situations where other drugs or underlying diseases appear to provide a more likely explanation for the observed event than the drug concerned).
- Disappearance of the event even though the trial drug treatment continues or remains unchanged.

Responsibilities for SAE reporting to Boehringer-Ingelheim (BI)

The Sponsor shall report (i.e., from signing the informed consent onwards through the protocol specified follow-up period after discontinuing spesolimab) all SAEs and non-serious AEs which are relevant for a reported SAE and Adverse Events of Special Interest (AESI) by fax or other secure method using BI IIS SAE form to the BI Unique Entry Point in accordance with timeline specified in the Safety Data Exchange Agreement.

BI Unique Entry point for SAE/AESI reporting:

[contact]

SAE/AESI reporting timelines

- within five (5) calendar days upon receipt of initial and follow-up SAEs containing at least one fatal or immediately life-threatening event;
- within ten (10) calendar days upon receipt of any other initial and follow-up SAEs and AESIs.

For each adverse event, the investigator will provide the onset date, end date, intensity, treatment required, outcome, seriousness, causality and action taken with the BI study drug. The investigator will determine the expectedness of the investigational drug to the AEs as defined in the Listed Adverse Events section of the Boehringer Ingelheim's (BI's) Investigator Brochure for the Product or Product Information (PI) for the authorized Study Drug provided by BI.

The investigator does not need to actively monitor patients for adverse events once the clinical trial has ended. However, if the investigator becomes aware of an SAE(s) that occurred after the patient has completed the clinical trial (including any protocol specified follow-up period), it should be reported to BI if investigator considers it as relevant to the BI study drug.

Pregnancy

In the rare case that a female subject participating in this clinical trial becomes pregnant after having taken trial medication, the Investigator must report immediately (within 24 hours) the drug exposure during pregnancy (DEDP) to the Sponsor's unique entry point. The Pregnancy Monitoring Form for Studies (Part A) should be used.

The outcome of the pregnancy associated with the drug exposure during pregnancy must be followed up and reported to the Sponsor's unique entry point on the Pregnancy Monitoring Form for Studies (Part B).

As pregnancy itself is not to be reported as an AE, in the absence of an accompanying SAE and/or AESI, only the Pregnancy Monitoring Form for Studies and not the SAE form is to be completed. If there is an SAE and/or AESI associated with the pregnancy an SAE form must be completed in addition.

STUDY WITHDRAWAL:

In the event a study subject wants to withdraw early from the study for any reason, the subject will be asked to return for an Early Termination visit (see above for procedures).

Table 2: TOTAL VOLUME OF BLOOD COLLECTED DURING THE STUDY:

		Treatment				Follow-Up
Visit	1 Screening	2 Baseline	3, 5, 7, 8, 9	4	6	10-13

Blood + Serum	23	32	15	20	23	23
Total volume	23	23	15	20	23	23

The total estimated blood volume is between 15 and 23 mL per month during treatment, and 23 mL per month during Follow-Up period. Additional volumes may be required for repeat testing or as part of unscheduled visits.

DISCONTINUATION OF TREATMENT AND WITHDRAWAL OF SUBJECTS:

The reasons why a subject may discontinue or be withdrawn from the study by the investigator include, but are not limited to the following: subject request, protocol violation, loss to follow up, subject non-compliance, significant worsening of subject's disease, study termination by investigators, and a confirmed grade 3 or higher adverse event (using Common Terminology Criteria for Adverse Events), which is suspected to be related to test article administration. Subjects that elect to withdraw from the trial due to lack of efficacy and/or exacerbation of disease will undergo an Early Termination visit (see Procedure Section and Schedule of Events)

Stopping Rules

Patients will be permanently discontinued from study treatment in the event of:

- Anaphylactic reaction or other severe systemic reaction to study drug injection
- Pregnancy at any time during the study period
- Diagnosis of a malignancy during study, excluding carcinoma in situ of the cervix, or squamous or basal cell carcinoma of the skin
- Treatment with any prohibited concomitant medication or procedure
- Any infection that is opportunistic, whose nature or course may suggest an immunocompromised status

Study drug dosing may be temporarily suspended in the event of:

- Intercurrent illnesses or major surgery
- An infection that requires systemic treatment with antibiotic, antifungal, antiviral, anti-parasitic, or anti-protozoal agents or requires oral treatment with such agents for longer than 2 weeks. Treatment of certain infections such as latent tuberculosis may be treated concurrently with spesolimab treatment

Duration of study drug suspension should be reviewed on a case-by-case basis and can be discussed with the PI.

In case of systemic hypersensitivity including infusion reactions and anaphylactic reaction, emerging during or after infusion/injection of study medication, the investigator should consider in accordance with severity of the reaction and local standard of care to:

- Immediately interrupt the infusion/injection

- Treat with systemic anti-histamines, intravenous steroids, and in case of a severe allergic reaction (e.g., anaphylactic reaction) epinephrine
- Blood draw for plasma sample of IgE and ADA/neutralizing antibody (Nab), serum tryptase, and complement components

In case of systemic hypersensitivity including infusion reactions, based on patient's clinical course and medical judgment, the infusion may be re-initiated in case of mild or moderate infusion reactions at lower speed with gradual increase to complete the infusion as detailed in the label. Regardless, the total duration of infusion should not exceed 180 minutes (3 hours).

Safety Evaluation

This is an open label, proof-of-concept study with an FDA-approved drug. Safety and tolerability will be evaluated from the AEs, limited physical examinations, and vital sign measurements. More frequent safety evaluations may be performed if clinically indicated or at the discretion of the investigator.

Aggregated AEs will be evaluated monthly by the PI/research teams.

Safety data will be reviewed by the investigators who will monitor the study on a regular basis and meet regularly (approximately once a month, depending on the number of subjects enrolled). The local IRBs, FDA, and Boehringer Ingelheim will be notified of adverse events (as required by each institution).

Physical Examination/Vital Signs

Qualified personnel will perform limited physical examinations, blood pressure and heart rate at each visit.

Limited physical examination consists of assessments of general appearance; skin; head, eyes, ears, nose, and throat (HEENT); heart; lungs; abdomen; extremities; neurological function; and lymph nodes.

MEASURES TO MINIMIZE/AVOID BIAS:

Subject Identification

Subjects are numbered sequentially. Each subject screened (total of 25 screened) will be assigned a unique screening number for the duration of the study. Subject screening numbers will also become a subjects treatment number if they are enrolled in the study after providing informed consent and meeting inclusion criteria. Subjects who discontinue or withdraw from the study before receiving a treatment assignment code, but re-enroll at a later time must be assigned a new screening number. The investigator must maintain a master log linking the subject number to the subject's name. The investigator must follow all applicable privacy laws in order to protect a subject's privacy and confidentiality.

INVESTIGATIONAL DRUG SUPPLY :

Eligible participants will receive 900 mg intravenous spesolimab starting at Visit 2/week 0/Baseline. All participants will receive a total of 8 or 9 infusions (depending on dosing frequency) through Week 28 or Week 26 (depending on whether the subject's dosing frequency is increased to every 3 weeks at Week 8), unless there is significant worsening. All subjects should be observed for 30 minutes following the infusion at Baseline to assess safety. Select cases will be offered the opportunity to continue treatment through Week 52 on case-by-case basis if the patient would benefit from continued treatment. All subjects who have not been discontinued will be monitored once a month, for 4 months after treatment cessation.

All study medication will be provided by Boehringer Ingelheim, refrigerated and stored between 2-8°C in a secure area. Study drug will be administered to subjects at each study visit in office. The investigative site will account for all study drug dispensed and stored during the study.

STATISTICAL CONSIDERATIONS:

Sample Size

This is a proof-of-concept, open-label trial. Twenty patients will be enrolled in the trial to demonstrate efficacy of spesolimab in a population of patients with moderate-severe, refractory PG. Although there is no formal power calculation, a sample size of n=20 subjects allows 81% power at 2.5% significance for a one-sided binomial test to detect at Week 16 a difference of 36.6% in the proportion of GPG success compared to a constant set to be equal to 10%. The choice of the constant was based on data from a randomized clinical trial for efficacy of infliximab where a group of 17 PG placebo-treated patients showed 6% response at Week 2 (Brooklyn et al.,2006).

Demographics and Other Baseline Characteristics

Descriptive statistics of demographics and other baseline characteristics of patients will be summarized with mean, median, and standard deviation for quantitative outcomes, and frequency and percentage tables for categorical outcomes.. Other baseline characteristics include sex, age, height, weight, vital signs, duration of PG, history of pathergy or PG trigger (if known), concurrent diagnoses from medical history and indications for concomitant medication, concomitant medication, and previous PG treatments.

Target Lesion Measurement and Digital Image Assessments

Size of target PG lesion will be approximated at each visit by measuring the length, width and depth of the lesion. Target lesion will also be analyzed using Image J software to obtain a more precise surface area of each lesion using digital photographs taken at each visit.

Analysis of Primary Endpoint

We will compare the proportion of patients achieving one-point decrease in target lesion GPG score at Week 16 with a constant p=0.10. Clopper-Pearson 90% confidence interval will be estimated.

Analysis of Secondary Endpoints

- One sided Clopper-Pearson 90% confidence intervals will be estimated for the proportion of patients achieving re-epithelization (GPG Severity Score of 0) at Visits 3, 4, 5, 6, 7, 8, and 9
- We will apply a two-sided paired t-test to evaluate significance of the mean difference of GPG score at Week 16 versus Week 0.
- Mean patient reported scores of pain (Pain VAS) and quality of life (DLQI) at baseline will be compared to those at Week 16 and treatment termination using the student's t- test to compare between subject's pre and post-treatment scores.
- One sided Clopper-Pearson 90% confidence intervals will be estimated for the proportion of patients with recurrence or worsening of PG lesions from point of complete re-epithelization or spesolimab cessation at end of treatment visit (Week 28 or Week 26 depending on dosing frequency).

Interim Analysis

An interim analysis will be performed after the first 10 subjects complete Week 16. We will continue enrollment during this time. Proportion of patients achieving one-point GPG score decrease will be reported. Changes from baseline at Week 16 in the PG lesions (number, size, GPG score) will be evaluated and reported. Enrolled subjects will continue to receive treatments during this time.

Data Transfer and Management

Data including the patient info, demographics, clinical scores will be stored in password-protected files that will be shared only with investigators and a biostatistical team, if necessary. Data will be stored on secure Mount Sinai servers that may only be accessed by investigators listed on this protocol.

Analysis of Safety and Tolerability

Safety will be evaluated by tabulations of adverse events (AEs) and will be presented with descriptive statistics at each visit. AEs will be coded using the CTCAE, Common Terminology Criteria for Adverse Events, V 4.0 and MedDRA. The number and percentage of subjects/lesions experiencing an AE/SAE will be stratified by system organ class, or a preferred term, and/or severity of the adverse event, and recorded and tabulated overall by each sub-strata. Each subject will be counted only once within a system organ class or a preferred term using the adverse events with the highest severity within each category. All information pertaining to adverse events noted during the study will be listed by subject, detailing verbatim given by the investigator, preferred term, system organ class, date of onset, date of resolution, severity, and relationship to treatment. A tabulation of AEs will be provided by subject.

Table 3. Schedule of Events Q4 Week Dosing Through Week 28

Visit Week	(Up to -28 Days before Baseline)	0	4	8	12	16	20	24	28	4 wk post-spesolimab last dose	8 wk post-spesolimab last dose	12 wk post-spesolimab last dose	16 wk post-spesolimab last dose		
Visit #	1	2	3	4	5	6	7	8	9	10	11	12	13		
Visit Type	Screening	Baseline	TX	TX	TX	TX	TX	TX	TX	F/Up	F/Up	F/Up	F/Up	Early Term (ET)	Additional Treatment Visits
Informed Consent	X														
Inclusion/Exclusion Criteria	X	X													
Demographics/Medical Hx ¹	X														
Limited Physical Exam	X	X													
Vitals ²	X	X	X	X	X	X	X	X	X					X	X
Serum Preg Test	X														
Urine Preg Test		X	X	X	X	X	X	X	X					X	X
CBC w/differential, CMP and CRP	X	X	X	X	X	X	X	X	X					X	X
Screening for TB (Quantiferon Gold, or PPD), HIV, HepB and HepC	X														
PG Clinical Assessments (including number location and measurements)	X	X	X	X	X	X	X	X	X	X	X	X	X	X	X
Global PG (GPG) Severity Score	X	X	X	X	X	X	X	X	X	X	X	X	X	X	X
Subject PG Questionnaire DLQI		X	X	X	X	X	X	X	X	X	X	X	X	X	X

Visit Week	(Up to -28 Days before Baseline)	0	4	8	12	16	20	24	28	4 wk post-spesolimab last dose	8 wk post-spesolimab last dose	12 wk post-spesolimab last dose	16 wk post-spesolimab last dose		
Visit #	1	2	3	4	5	6	7	8	9	10	11	12	13		
Visit Type	Screening	Baseline	TX	TX	TX	TX	TX	TX	TX	F/Up	F/Up	F/Up	F/Up	Early Term (ET)	Additional Treatment Visits
Standardized Photographs		X	X	X	X	X	X	X	X	X	X	X	X	X	X
Record and changes related to associated conditions (such as IBD, RA, etc) if applicable		X	X	X	X	X	X	X	X	X	X	X	X	X	
Serum Cytokine Profile O-Link Inflammatory Panel		X				X				X	X	X	X	X	
Pharmacokinetics, ADA, NAb		X		X		X			X					X	
Dispense Drug		X	X	X	X	X	X	X	X						
Concomitant Medications	X ⁴	X	X	X	X	X	X	X	X	X	X	X	X	X	X
Adverse Events	X	X	X	X	X	X	X	X	X	X	X	X	X	X	X

¹ Includes current and past medical conditions in addition to personal and family history of inflammatory bowel disease, rheumatoid arthritis, and autoimmune conditions as well as history of myeloproliferative disorders and malignancy

² Includes height and weight (only at screening), blood pressure, and pulse

³ Pre-dose PK, ADA, NAb samples will be obtained at selected visits (Visit 2, 4, 6, and 9 or ET). At Week 0/Visit 2, a post-dose PK samples will also be obtained approximately 5 mins after end of i.v. infusion.

⁴ Record all concomitant medications at each visit, and at screening also collect any medications taken within the last 30 days, and previous therapies/treatments for PG (including systemic and topical treatments, and invasive treatment such as surgery, radiation and cryotherapy).

Table 4. Schedule of Events Q4 Week Dosing through Week 8 Followed by Q3 Week Dosing Through Week 26

Visit Week	(Up to -28 Days before Baseline)	0	4	8	11	14	16	17	20	23	26	4 wk post-spesolimab last dose	8 wk post-spesolimab last dose	12 wk post-spesolimab last dose	16 wk post-spesolimab last dose		
Visit #	1	2	3	4	5	6	7	8	9	10	11	12	13	14	15		
Visit Type	Screening	Baseline	TX	TX	TX	TX		TX	TX	TX	TX	F/Up	F/Up	F/Up	F/Up	Early Term (ET)	Additional Treatment Visits
Informed Consent	X																
Inclusion/Exclusion Criteria	X	X															
Demographics/Medical Hx ¹	X																
Limited Physical Exam	X	X															
Vitals ²	X	X	X	X	X	X	X	X	X	X	X					X	X
Serum Preg Test	X																
Urine Preg Test		X	X	X	X	X	X	X	X	X	X					X	X
CBC w/differential, CMP and CRP	X	X	X	X	X	X	X	X	X	X	X					X	X
Screening for TB (Quantiferon Gold, or PPD), HIV, HepB and HepC	X																
PG Clinical Assessments (including number, location and measurements)	X	X	X	X	X	X	X	X	X	X	X	X	X	X	X	X	X
Global PG (GPG) Severity Score	X	X	X	X	X	X	X	X	X	X	X	X	X	X	X	X	X
PG Questionnaire		X	X	X	X	X	X	X	X	X	X	X	X	X	X	X	X

Visit Week	(Up to -28 Days before Baseline)	0	4	8	11	14	16	17	20	23	26	4 wk post-spesolimab last dose	8 wk post-spesolimab last dose	12 wk post-spesolimab last dose	16 wk post-spesolimab last dose		
Visit #	1	2	3	4	5	6	7	8	9	10	11	12	13	14	15		
Visit Type	Screening	Baseline	TX	TX	TX	TX		TX	TX	TX	TX	F/Up	F/Up	F/Up	F/Up	Early Term (ET)	Additional Treatment Visits
Standardized Photographs		X	X	X	X	X	X	X	X	X	X	X	X	X	X	X	X
Record and changes related to associated conditions (such as IBD, RA, etc) if applicable		X	X	X	X	X	X	X	X	X	X	X	X	X	X	X	
Serum Cytokine Profile O-Link Inflammatory Panel		X					X					X	X	X	X	X	
Pharmacokinetics, ADA, NAb ³		X		X			X				X					X	
Dispense Drug		X	X	X	X	X	X	X	X	X	X						
Concomitant Medications	X ⁴	X	X	X	X	X	X	X	X	X	X	X	X	X	X	X	X
Adverse Events	X	X	X	X	X	X	X	X	X	X	X	X	X	X	X	X	X

¹ Includes current and past medical conditions in addition to personal and family history of inflammatory bowel disease, rheumatoid arthritis, and autoimmune conditions as well as history of myeloproliferative disorders and malignancy

[figure not shown]
² Includes height and weight (only at screening), blood pressure, and pulse

³ Pre-dose PK, ADA, NAb samples will be obtained at selected visits (Visit 2, 4, 7 and 11, or ET). At Week 0/Visit 2, a post-dose PK samples will also be obtained approximately 5 mins after end of i.v. infusion.

⁴ Record all concomitant medications at each visit, and at screening also collect any medications taken within the last 30 days, and previous therapies/treatments for PG (including systemic and topical treatments, and invasive treatment such as surgery, radiation and cryotherapy).

Figure 3. Flow Diagram for Participants

REFERENCES

- ¹ Alavi, A., French, L. E., Davis, M. D., Brassard, A., & Kirsner, R. S. (2017). Pyoderma gangrenosum: an update on pathophysiology, diagnosis and treatment. *American journal of clinical dermatology*, 18(3), 355-372.
- ² Xu, A., Balgobind, A., Strunk, A., Garg, A., & Alloo, A. (2020). Prevalence estimates for pyoderma gangrenosum in the United States: an age-and sex-adjusted population analysis. *Journal of the American Academy of Dermatology*, 83(2), 425-429.
- ³ Cozzani, E., Gasparini, G., & Parodi, A. (2014). Pyoderma gangrenosum: a systematic review. *G Ital Dermatol Venereol*, 149(5), 587-600.

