ENDPOINTS:

Primary Endpoint

- One point decrease from baseline in target lesion Global PG (GPG) Severity Score at Week 16

Secondary Endpoints

- Complete re-epithelization of PG lesions (GPG Severity Score of 0) at visits 3, 4, 5, 6, 7, 8, and 9.
- Absolute change from baseline in patient-reported pain severity (Pain-VAS) at visits 3, 4, 5, 6, 7, 8, and 9 and at complete re-epithelization of ulcer.
- Absolute change in quality of life (DLQI) from baseline at visits 3, 4, 5, 6, 7, 8, and 9 and at complete re-epithelization of ulcer.
- Recurrence of PG lesions after complete re-epithelization (GPG score 0) of all lesions and spesolimab cessation

- Time to worsening (1 or more GPG point increase) of target PG lesion from spesolimab cessation

STUDY DESIGN OVERVIEW:

This study is a prospective, proof-of-concept, open label clinical trial. The study will take place at Icahn School of Medicine at Mount Sinai.

The study will screen up to 25 subjects in order to enroll a total of up to 20 patients with at least one clinically measurable ulcerative PG lesion. Subjects will receive 900 mg of spesolimab intravenously (IV) over 90 minutes at a frequency of every 4 weeks until Week 28 with the following exceptions:

- At the Week 8 visit, subjects who do not show any improvement, show only minimal improvement, or those that begin to lose their initial improvement response (decrease in pain or wound drainage), may be switched to a dosing frequency of every 3 weeks through Week 26, at the discretion of the investigator. These subjects will still return at Week 16 for an endpoint visit, but will not receive treatment at this visit. Refer to Tables 3 and 4 for schedule of events.

All subjects will be monitored monthly for 4 months subsequent to treatment cessation.

Subjects who reach GPG score 0 at anytime during the study will continue to receive treatments until week 28 (or Week 26 depending on dosing frequency) and will then be monitored for 4 months subsequent to treatment cessation.

Subjects who are experiencing improvement in their PG but who have not reached complete wound healing will continue treatment until Week 28 (or Week 26 for those who were switched to every 3 week dosing), even if primary endpoint has been achieved. These subjects will then be monitored for 4 months subsequent to treatment cessation.

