- Urine pregnancy test for all female subjects of child-bearing potential to confirm subject is not pregnant
- Collect blood samples for CBC with differential, CMP, and C-reactive protein (CRP), serum cytokine profiling (O-link® inflammatory cytokine panel, IL-1 β , and IL-36 subtypes), Nab, ADA, and Pre- and post dose pharmacokinetics.
- Administer study drug

Spesolimab Treatment Phase

Visits 3 thru 9 (subjects that dose every 4 weeks) or Visits 3 thru 11 (subjects that are switched to every 3 week dosing at Week 8)

- Record concomitant medications (including use of pain medication) and adverse events
- Urine pregnancy test for all female subjects of child-bearing potential to confirm subject is not pregnant
- Patient Pyoderma Gangrenosum Questionnaires and DLQI
- Obtain vital signs
- Standardized clinical photography of target lesion and other PG lesions
- PG clinical assessments (including number/location/measurements of PG lesions and GPG score for target lesion)
- Assess status of associated comorbid conditions (improved, no change, worse)
- Collect blood samples for CBC with differential, CMP, and C-reactive protein (CRP)
- **Only at Week 8 and Week 28 (subjects dosed every 4 weeks) or Week 26 (subjects switched to dosing every 3 weeks):** Nab, ADA, and pre dose pharmacokinetics.
- **Only at Week 16:** serum cytokine profiling (O-link® inflammatory cytokine panel, IL-1 β , and IL-36 subtypes), Nab, ADA, and pre dose pharmacokinetics.
- Administer study drug

Post-Spesolimab Follow-up Phase

Visits 10 thru 13 (subjects dosed every 4 weeks) or Visits 12-15 (subjects switched to dosing every 3 weeks)

Follow-Up Visits at 1 Month, 2 Months, 3 Months and 4 Months Post-Spesolimab Treatment Cessation

- Record concomitant medications (including use of pain medication) and adverse events
- Patient Pyoderma Gangrenosum Questionnaires and DLQI
- Assess status of associated comorbid conditions (improved, same, worse)
- Standardized clinical photography of target lesion and other PG lesions

- PG clinical assessments (including number/location/measurements of PG lesions, and GPG score of target lesion)
- Collect blood for serum cytokine profiling (O-link® inflammatory cytokine panel, IL-1 β , and IL-36 subtypes)
- If subject worsens or sees progression of their PG during the 4- month follow-up period (defined as 1 or more increase in GPG score of target lesion), then patient will be discontinued from the study and started on available, standard PG therapies.

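### GPG response is analysed only at Week 16, and healing is tied to Visits 3-9, which end at Week 28 on one schedule and Week 20 on the other, so outcome after the planned course is under-reported

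*Combined protocol and SAP*

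**What the plan says.** **GPG response.** The primary endpoint is "One point decrease from baseline in target lesion Global PG (GPG) Severity Score at Week 16". The Analysis of Secondary Endpoints adds a "two-sided paired t-test to evaluate significance of the mean difference of GPG score at Week 16 versus Week 0". The interim analysis also uses Week 16.

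**Healing, pain and quality of life.** The healing endpoint is "Complete re-epithelization of PG lesions (GPG Severity Score of 0) at visits 3, 4, 5, 6, 7, 8, and 9". In the Endpoints section, Pain-VAS and DLQI change use the same visit list, plus the time of complete re-epithelization. In the analysis section, mean Pain-VAS and DLQI "at baseline will be compared to those at Week 16 and treatment termination".

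**Dosing.** Investigational Drug Supply states: "All participants will receive a total of 8 or 9 infusions (depending on dosing frequency) through Week 28 or Week 26". Procedures gives the treatment phase as "Visits 3 thru 9 (subjects that dose every 4 weeks) or Visits 3 thru 11", the longer range being for subjects switched at Week 8. The Study Design Overview continues dosing in subjects who have already met the primary endpoint. Selected subjects may be treated up to Week 52.

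**Data collected.** GPG is scored at every treatment visit. The four monthly follow-up visits include "PG clinical assessments (including number/location/measurements of PG lesions, and GPG score of target lesion", together with the patient questionnaires and DLQI.

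**Recurrence and worsening.** In the Endpoints section, recurrence requires both healing of all lesions and stopping spesolimab, and time to worsening is counted from stopping. The Analysis of Secondary Endpoints counts recurrence or worsening from either healing or stopping.

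**The concern.** A reader of the final report will want to know how many subjects responded, and how many healed, on the regimen that was given. The plan reports response at about the midpoint of dosing. It reports healing through a list of visit numbers that suits only one of the two schedules.

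Subjects are switched because they have improved little or are losing an early response, so late readings matter most in them. Their healing endpoint nevertheless stops six weeks before their last dose.

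The Study Design Overview expects some subjects to lose an initial response, yet the Endpoints section defines no measure of lost response while treatment continues. A subject who enters at GPG 4, is at 3 at Week 16 and is back at 4 at the last dosing visit is a primary-endpoint responder. That subject meets neither the recurrence nor the time-to-worsening definition during treatment.

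**Working it through.** **1. Infusion count (the plan's own figure).** From Tables 3 and 4:

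- Every 4 weeks: Weeks 0, 4, 8, 12, 16, 20, 24, 28 = 8 infusions.
- Switched at Week 8: Weeks 0, 4, 8, 11, 14, 17, 20, 23, 26 = 9 infusions.

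This reproduces the stated 8 or 9, provided that the Week 16 visit of the switched schedule is untreated, as the Study Design Overview says. Table 4 marks drug at that visit, which would make 10. Those passages must be reconciled; the count below follows the stated total of 9.

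**2. What each visit number means.**

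| Visit | Table 3 | Table 4 |
|---|---|---|
| 3 | Week 4 | Week 4 |
| 4 | Week 8 | Week 8 |
| 5 | Week 12 | Week 11 |
| 6 | Week 16 | Week 14 |
| 7 | Week 20 | Week 16 |
| 8 | Week 24 | Week 17 |
| 9 | Week 28 (last dose) | Week 20 |
| 10 | 4 weeks after last dose | Week 23 |
| 11 | 8 weeks after last dose | Week 26 (last dose) |
| 12 | 12 weeks after last dose | 4 weeks after last dose |

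From Visit 5 on, no visit number means the same week in both schedules. At Visit 9 the gap is 28 − 20 = 8 weeks.

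**3. Infusions given before each reading.** The protocol does not say that GPG is scored before the infusion; only the PK, ADA and NAb samples are labelled pre-dose. Procedures lists drug administration last, so scoring first is an inference from list order. On that assumption:

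| Reading | Every 4 weeks | Switched |
|---|---|---|
| Week 16 (GPG response, mean GPG) | 4 of 8 | 5 of 9 |
| Visit 9 (last healing reading) | 7 of 8 | 6 of 9 |
| Infusions with no later healing reading | 8 − 7 = 1 (Week 28) | 9 − 6 = 3 (Weeks 20, 23, 26) |

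If scoring followed the infusion on the same day, the Week 16 count on the 4-weekly schedule would be 5 of 8. Visit 9 would then follow 8 of 8 or 7 of 9, but a same-day score could hardly show healing from that day's dose.

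**4. Unused readings.** The first follow-up visit is four weeks after the last dose: 28 + 4 = Week 32 (Visit 10, Table 3) or 26 + 4 = Week 30 (Visit 12, Table 4). GPG, pain and DLQI are collected there. No response or healing endpoint uses it, and none uses Visits 10 and 11 of Table 4.

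**5. Possible size.** With 20 subjects, one subject is 1/20 = 5 percentage points, so one or two late closures would change a healing rate by 5 to 10 points.

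For loss of response, take the plan's 90% Clopper-Pearson interval: lower limit = 5th percentile of Beta(x, n − x + 1), upper limit = 95th percentile of Beta(x + 1, n − x).

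- 7/20 (35%): 17.7% to 55.8%, which excludes 10%.
- 4/20 (20%), if three of the seven lost response by Week 28: 7.1% to 40.1%, which does not.

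This is an illustration only. The documents give no rate of on-treatment loss and plan no comparison with 10% at Week 28.

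**The case against.** The strongest reply is that this is a 20-subject, open-label proof-of-concept trial with one pre-stated primary time point, and that ending a secondary endpoint on the last treatment visit is a defensible choice. That stands for Table 3. It does not cover Table 4, where Visit 9 is not the last treatment visit.

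Three stronger readings are tempting, and the documents do not support them.

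- *The full course is never evaluated, or the final infusion cannot affect any efficacy endpoint.* On the 4-weekly schedule GPG 0 is read at Week 28, after 7 of 8 infusions. Pain and DLQI are compared at treatment termination. Recurrence and time to worsening are secondary endpoints read after the last dose.
- *Relapse on treatment is invisible.* GPG 0 by visit would show a net loss of healing. The recurrence analysis, worded with healing or cessation, can count a healed ulcer that reopens on drug. Worsening of the underlying disease is recorded as an adverse event, and significant worsening leads to discontinuation. What remains uncovered is the partial responder who drifts back; an adverse-event listing does not give a durability rate.
- *The reported rates are biased.* A proportion labelled Week 16 does not misstate Week 16, and GPG 0 at Week 28 does not understate healing at Week 28. The plan defines no ever-healed rate. The fault is omission and, for visit numbers, pooling of unlike weeks.

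A further fair point is that treatment may be extended to Week 52. A reading four weeks after the last dose could then fall as late as 52 + 4 = Week 56, so a single post-treatment time point would mix different exposures unless extended subjects are shown apart.

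**Conclusion.** The point holds as a gap in the secondary analyses. It does not challenge the primary endpoint.

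- The one-point response (read here as a decrease of at least one point) and mean GPG change are analysed only at Week 16, after 4 of 8 or 5 of 9 infusions.
- The visit-numbered endpoints stop at Week 28 in one schedule and Week 20 in the other. In switched subjects three infusions have no later healing reading, and Visits 5 to 9 pool different weeks.
- No response or healing endpoint is read after the last infusion, although the data are collected.
- On-treatment loss of response in a subject who never reached GPG 0 is not a defined efficacy endpoint, and the Endpoints and analysis sections disagree on when recurrence counts.

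The infusion counts assume scoring before the infusion and no dose at the switched schedule's Week 16 visit. The visit-number mismatch needs neither assumption. How far the results would move is unknown beyond 5 points per subject, because the documents give no rate of late healing or late loss and do not say how many subjects will switch.

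**What to change.** Keep Week 16 as the primary time point and change the secondary analyses as follows.

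1. Define secondary time points by study week and by end of scheduled treatment (Week 28 or Week 26), not by visit number.
2. Report GPG response and GPG 0 with exact intervals, and Pain-VAS and DLQI change, at each scheduled week, at the last scheduled dosing visit, and at the first follow-up visit four weeks after the last dose (Visit 10 in Table 3, Visit 12 in Table 4).
3. Report the share of Week 16 responders still responding at those last two time points.
4. For the binary outcomes, count subjects who left early as non-responders.
5. Show subjects treated beyond Week 28 or 26 separately at the post-treatment reading.
6. Reconcile the recurrence definition between the Endpoints section and the Analysis of Secondary Endpoints.

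The cost is analysis wording and one or two more descriptive tables. No visit or sample is added and dosing is untouched. These tables describe durability and late healing; they would support no confirmatory claim.
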